7. STUDY POPULATION

7.1. Number of Subjects and Sites

The study population consists of Dose Escalation Phase (Phase 1) subjects who were enrolled under previous amendments and were ongoing during Amendment 6, version dated 06 Jun 2017. As of 05 Jul 2018, enrollment of new subjects into Phase 1 has been discontinued and Phase 2 will not proceed.

Depending on the tolerability of each dose level, this study will enroll approximately 158 (136-182) subjects. The Dose Escalation Phase will include the following:

- Arm A: 20 subjects
- Arm B: 24 (18 to 36) subjects
- Arm C: 24 (18 to 36) subjects

The Dose Expansion Phase may enroll up to 50 subjects in Arm B and/or 40 subjects in Arm C for a total of up to 90 subjects.

Subjects will be enrolled in the US, Canada and Europe.

7.2. Inclusion Criteria

As of 05 Jul 2018, enrollment of new subjects into Phase 1 has been discontinued and Phase 2 will not proceed.

Subjects must satisfy the following criteria to be enrolled in the study:

1. Subjects \geq 18 years age and \leq 80 years of age at the time of signing the informed consent form.
2. Understand and voluntarily sign an informed consent form prior to any study related assessments/procedures being conducted.
3. Able to adhere to the study visit schedule and other protocol requirements.
4. Must have a documented diagnosis of CLL/SLL requiring treatment (IWCLL Guidelines for the Diagnosis and Treatment of CLL [Hallek, 2008]). In addition:
 - a. Presence of at least one clinically measurable lesion:
 - i. nodal lesion that measures \geq 1.5 cm in longest dimension (LD) and \geq 1.0 cm in longest perpendicular dimension (LPD), or
 - ii. spleen that measures \geq 14 cm in longest vertical dimension (LVD) with a minimum of 2 cm enlargement, or
 - iii. liver that measures \geq 20 cm in LVD with a minimum of 2 cm enlargement, or
 - iv. peripheral blood B lymphocyte count $>$ 5000/uL

5. Must meet the criteria for relapsed and/or refractory disease according to the IWCLL guidelines [REDACTED] to ≥ 1 prior treatment (with the exception of Arm B) and have evidence of disease progression requiring treatment at the time of study entry as follows:

a. For Arms A and C, subjects must have received either prior chemoimmunotherapy or therapy with an approved BTK inhibitor with the following exceptions:

i. Chemoimmunotherapy is not required if subjects have specific co-morbidities that preclude the use of standard chemoimmunotherapy meeting at least 1 of the following criteria;

1. CIRS ≥ 6 ;
2. Creatinine Clearance < 70 mL/min;
3. Subject is not a candidate for a chemoimmunotherapy in the opinion of investigator.

The reason for not being a candidate must be documented in the CRF.

ii. Treatment with an approved BTK inhibitor is not required if subject has contraindications or is not a candidate for such a therapy in the opinion of the investigator.

The reason for not being a candidate must be documented in the CRF.

b. For Arm B, subjects with treatment-naïve or R/R CLL must meet the following criteria:

i. Dose Escalation Phase: Subjects must not have received prior treatment with ibrutinib (or any other BTK inhibitors) and must have:

1. R/R CLL: has 17p- and/or TP53 mutation; or
2. Treatment naïve: is unfit for standard chemoimmunotherapy meeting at least 1 of the following co-morbidity criteria:

- a. CIRS ≥ 6 ;
- b. Creatinine Clearance < 70 mL/min;
- c. Subject is not a candidate for a chemoimmunotherapy in the opinion of the investigator.

The reason for not being a candidate must be documented in CRF.

ii. Dose Expansion Phase: Subjects must not have received prior treatment with ibrutinib (or any other BTK inhibitors) and must have high risk CLL. High risk is defined as:

- 1) 17p- and/or TP53 mutation positive in treatment naïve CLL; or
- 2) 17p- and/or TP53 mutation positive, and/or complex karyotype, and/or progression < 24 months after completion of 1st line chemoimmunotherapy in R/R CLL

- c. Subjects with R/R SLL or CLL with bulky disease (at least one lymph node measuring > 5.0 cm in diameter) are considered at higher risk for developing TFR and may only be enrolled upon discussion with the sponsor's medical monitor and agreement to close medical management.
- 6. Subjects must have the following lab values:
 - a. Absolute neutrophil count (ANC) $\geq 1,500$ cells/mm³ or ≥ 1000 cells/mm³ if secondary to bone marrow involvement by disease.
 - b. Platelet count $\geq 100,000$ cells/mm³ (100×10^9 /L) or $\geq 50,000$ cells/mm³ (50×10^9 /L) if secondary to bone marrow involvement by disease.
 - c. Serum aspartate transaminase (AST/SGOT) or alanine transaminase (ALT/SGPT) $< 3.0 \times$ upper limit of normal (ULN) unless due to disease.
 - d. Serum bilirubin $< 1.5 \times$ ULN unless due to Gilbert's syndrome.
 - o Serum bilirubin $\leq 1.0 \times$ ULN unless due to Gilbert's syndrome,
Treatment Arm B only (CC-122 in combination with ibrutinib)
 - e. Calculated creatinine clearance of ≥ 60 ml/min.
 - f. No evidence of TLS per the Cairo-Bishop definition of laboratory TLS ([Appendix E](#)) (subjects may be enrolled upon correction of electrolyte abnormalities).

8. Ability to swallow oral capsules without difficulty.

9. Pregnancy Prevention Risk Management Plan:

- a. Females of childbearing potential (FCBP) must undergo pregnancy testing based on the frequency outlined in the PPRMP and pregnancy results must be negative.
- b. Unless practicing complete abstinence from heterosexual intercourse, sexually active FCBP must agree to use adequate contraceptive methods as specified in the PPRMP.
 - o For Arm C, subjects must agree to use adequate contraceptive methods for 18 months (please refer to the obinutuzumab IB, PI, and SmPC).
 - Complete abstinence is only acceptable in cases where this is the preferred and usual lifestyle of the subject.
 - Periodic abstinence (calendar ovulation, symptothermal, post-ovulation methods) and withdrawal **are not acceptable**.
- c. Males (including those who have had a vasectomy) must practice complete abstinence or use barrier contraception (condoms) when engaging in sexual activity with FCBP as specified in the PPRMP.
- d. Males must agree not to donate semen or sperm for the duration of the study and for 3 months after the last dose of CC-122.
- e. All subjects must:
 - Understand that the IP could have a potential teratogenic risk.

- Agree to abstain from donating blood while taking IP and following discontinuation of IP.
- Agree not to share IP with another person.
- f. Other than the subject, FCBP and males should not handle the IP or touch the capsules, unless gloves are worn.
- g. Be counseled about pregnancy precautions and risks of fetal exposure (see Section 6.1.13).

Arm B only:

10. Enrollment into Arm B will be permitted if ibrutinib is considered the standard of care in the clinical practice.

Expansion Cohort 2 of Arm C:

11. Subjects in Cohort 2 of Arm C must meet the following criteria:

- a. Subject must have received at least one BCR PI (ibrutinib, idelalisib, or other approved BTK or PI3K inhibitor) and/or venetoclax;
- b. Subject must be either resistant to or intolerant of (ie., treatment failures) the last BCR PI and/or venetoclax. Resistant is defined as relapsed or refractory per IWCLL2008:
 - i. Relapse is defined as a patient who has previously achieved a CR or PR, but after a period of 6 or more months, demonstrates evidence of disease progression.
 - ii. Refractory is defined as failing to achieve a CR or PR, or disease progression within 6 months after initiation of treatment with an approved BTK or PI3K inhibitor (eg, ibrutinib, idelalisib) or venetoclax.
 - iii. Intolerance is defined as the inability to continue treatment with a BCR PI or venetoclax due to toxicities or due to development of a contraindication that makes the subject ineligible to receive further treatment with a BCR PI or venetoclax.

7.3. Exclusion Criteria

As of 05 Jul 2018, enrollment of new subjects into Phase 1 has been discontinued and Phase 2 will not proceed.

The presence of any of the following will exclude a subject from enrollment:

1. Any significant medical condition, laboratory abnormality, or psychiatric illness that would prevent the subject from participating in the study.
2. Any condition including the presence of laboratory abnormalities, which places the subject at unacceptable risk if he/she were to participate in the study.
3. Any condition that confounds the ability to interpret data from the study.

4. Prior autologous or allogeneic stem cell transplant (SCT)/bone marrow transplant within 12 months of signing the ICD. Subjects who received allogeneic SCT \geq 12 months before signing the ICD may be eligible provided there is no ongoing graft-versus-host disease and no ongoing immune suppression therapy.
5. Uncontrolled intercurrent illness including, but not limited to:
 - a. Ongoing or active infection requiring parenteral antibiotics.
 - b. Uncontrolled diabetes mellitus.
 - i. The glycemic targets for subjects with diabetes should take into consideration age, comorbidities, life expectancy, and functional status of the subjects and follow established guidelines (eg, International Diabetes Federation, the European Diabetes Working Party guidelines, and the American Diabetes Association). For younger (< 70 years old) or subjects with life expectancy \geq 10 years, the target glycosylated hemoglobin, type A1C (HbA_{1c}) should be < 7.0%. The target HbA_{1c} for older (\geq 70 years old) subjects or subjects with life expectancy < 10 years should be < 8.0%. Consultation with an endocrinologist is recommended when deciding if diabetes is optimally controlled. Subjects with a stable HbA_{1c} greater than the suggested target may be enrolled upon discussion with the medical monitor.
 - c. Chronic symptomatic congestive heart failure (Class III or IV of the New York Heart Association Classification for Heart Disease).
 - d. Active central nervous system involvement as documented by spinal fluid cytology or imaging.
 - e. Uncontrolled autoimmune hemolytic anemia or thrombocytopenia.
 - f. Other concurrent severe and/or uncontrolled concomitant medical conditions that could cause unacceptable safety risks or compromise compliance with protocol.
6. History of second malignancies with life expectancy of < 2 years or requirement of therapy that would confound study results. This does not include the following:
 - a. Basal cell carcinoma of the skin.
 - b. Squamous cell carcinoma of the skin.
 - c. Carcinoma in situ of the cervix.
 - d. Carcinoma in situ of the breast.
 - e. Carcinoma in situ of the bladder.
 - f. Incidental histologic finding of prostate cancer (TNM stage of T1a or T1b).
7. Known seropositivity for or history of active viral infection with human immunodeficiency virus (HIV), or hepatitis B or C virus (HBV, HCV).
 - a. Hepatitis B screening is mandatory for all patients (HBsAg and anti-HBc). Patients with active hepatitis B disease should not be treated with obinutuzumab. Patients should be referred to a specialist if they are carriers before treatment

starts (see PI or SmPC). Subjects who are positive for anti-HBC and/or anti-HBs but negative for HBsAg and HBV DNA may be treated after consultation with a hepatologist.

8. Any peripheral neuropathy \geq NCI CTCAE Grade 2.
9. Use of systemic corticosteroids in doses greater than prednisone equivalent to 20 mg/day.
10. Medicines with high probability to cause QT prolongation or torsades de pointes.
Subjects on chronic medications in this category may enroll after discussion with the medical monitor if changing these medications are not in the best medical interest of the patient.
11. History of hypersensitivity to IMiDs® (lenalidomide, pomalidomide, thalidomide).
12. Impaired cardiac function or clinically significant cardiac diseases, including any of the following:
 - a. LVEF $<$ 45% as determined by MUGA scan or ECHO.
 - b. Complete left bundle branch, or bifascicular, block.
 - c. Congenital long QT syndrome.
 - d. Persistent or uncontrolled ventricular arrhythmias or atrial fibrillation.
 - e. QTcF $>$ 470 msec on Screening ECG (mean of triplicate recordings).
 - f. Unstable angina pectoris or myocardial infarction \leq 6 months prior to starting CC-122.
 - g. Uncontrolled congestive heart failure or uncontrolled hypertension.
 - h. Troponin-T value >0.4 ng/mL or BNP >300 pg/mL.

Subjects with baseline troponin-T $>$ ULN or BNP >100 pg/mL are eligible but should have cardiologist evaluation prior to enrollment in the trial for baseline assessment and optimization of cardioprotective therapy and after discussion with the sponsor's medical monitor.

13. Chemotherapy, radiotherapy, investigational anticancer therapy or major surgery within 28 days of Day 1 dosing with the following exceptions:
 - a. Arm A: A minimum 5-day washout after discontinuation of ibrutinib (or other BTK inhibitors) is required; only those subjects without rapid disease progression during the 5-day washout will be allowed to enroll into Arm A.
 - i. Rapid disease progression is defined as follows:
 1. For subjects with measurable nodal disease, the increase in the sum of diameters of the largest lymph nodes (up to 3 nodes) exceeds 1 cm per day OR the diameter of the largest lymph node exceeds 5 cm during the 5 day wash out.
 2. For subjects with lymphocytosis, the increase in the ALC exceeds $2 \times 10^9/L$ per day OR the ALC exceeds $100,000 \times 10^9/L$ during the 5-day wash out;

- b. Arm C: No minimum washout is required after discontinuation of ibrutinib (or other BTK inhibitors)
- c. Approved PI3 kinase inhibitors: Subjects may start study treatment within 3 days of discontinuation of approved PI3 kinase inhibitors.

14. Persistent diarrhea or malabsorption \geq NCI CTCAE Grade 2, despite medical management.
15. Active disease transformation (ie, Richter's Syndrome); subjects with Richter's Syndrome that has resolved $>$ 2 years from signing the ICD are eligible.
16. Known acute or chronic pancreatitis
17. Pregnant or lactating females

Arm B only (CC-122 in combination with ibrutinib):

18. Prior treatment with a BTK inhibitor
19. Presence of transfusion-dependent thrombocytopenia or a history of bleeding disorders or clinical conditions (eg, gastrointestinal bleeding or constitutional disorders) that may increase risk of life-threatening bleeding when thrombocytopenic
20. History of stroke or intracranial hemorrhage within 6 months prior to signing the ICD
21. Medications that are strong inhibitors or inducers of CYP3A4/5 (eg, itraconazole, ketoconazole, clarithromycin, ritonavir, phenytoin, pentobarbital, and rifampin) should be changed; subjects who cannot change these medications must be excluded (see Appendix H for a list of strong and moderate inhibitors/strong inducers of CYP3A).
22. Use of concomitant anticoagulation with warfarin or other vitamin K antagonists is prohibited, as is treatment with these agents in the 7 days prior to signing the ICD. The use of other anticoagulants (eg, heparins) and anti-platelet agents is allowed per investigator's discretion. Investigator questions regarding this should be addressed to the sponsor's medical monitor or the study national Principal Investigators.

Arm C only (CC-122 in combination with obinutuzumab):

23. Hypersensitivity to obinutuzumab

8. DESCRIPTION OF STUDY TREATMENTS

8.1. Description of Investigational Products

8.1.1. CC-122

Celgene Corporation will supply CC-122 in appropriate strengths. The active pharmaceutical ingredient in capsules (AIC) was employed from the beginning of the current study (non-formulated, white opaque gelatin capsules). There are no other excipients in the capsules.

During the course of the current study, a new formulation, Formulation 6 [F6] of CC-122 is being developed at various strengths (0.5 mg, 1.0 mg, 1.5 mg, 2.0 mg, 2.5 mg, 3.0 mg, 3.5 mg, 4.0 mg) to be made available over the course of the study. The F6 formulations have different CC-122 base free amounts compared to the CC-122 AIC that was employed from the beginning of the current study. CC-122 AIC 0.5, 1, and 3 mg strengths were based on CC-122 HCl and are equivalent to 0.44, 0.88, and 2.64 mg CC-122 base free, respectively. CC-122 formulated capsules of 0.5, 1, 1.5, 2, 2.5, 3, 3.5 and 4 mg strengths are based on CC-122 base free and are equivalent to 0.56, 1.13, 1.69, 2.25, 2.81, 3.38, 3.95 and 4.51 mg CC-122 HCl, respectively.

Study CC-122-CP-002 Part 2 was an open-label, randomized, three-period, six-sequence, three-way single-dose crossover study in healthy adult subjects to evaluate the PK of CC-122 after administration of formulated (test formulations: Formulation 4 [F4] and F6) and AIC CC-122 capsules.

Following a single oral administration of CC-122 at the dose level of 3 mg from reference AIC formulation and formulated capsule F-6 formulation in healthy adult subjects (N=18), the total plasma exposures (AUC_{inf}) is 16.29% higher and the peak plasma exposure (C_{max}) is 35.58% higher from the F-6 formulation as compared to that from the reference AIC formulation. The CC-122 F-6 formulation has been selected for further development ([Data on File, 2015](#)).

For subjects on Arm A, subjects who start with AIC will continue to receive AIC; subjects who start with F6 will continue to receive F6 for all dose levels.

For subjects on Arms B and C, F6 will be introduced in the 1.0 mg cohorts after the 0.5 mg AIC fixed-dose cohort has been completed, and will continue to receive F6 thereafter. The 0.5 mg fixed dose cohorts will use AIC. Any subjects requiring doses of 0.25 mg or lower due to dose reductions will use AIC.

The formulated capsules will be provided in reddish brown gelatin capsules and contain the following excipients: Avicel PH 102, spray dried mannitol, crospovidone, areosil, and stearic acid.

Celgene will continue to provide up to 24 cycles of CC-122 for ongoing patients experiencing clinical benefit.

Please refer to the CC-122 IB and pharmacy manual for detailed information concerning the physical properties of CC-122.

The IP will be labeled per local regulations. Store as directed on package label.

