8.2. Cumulative Dose and Dose Intensity

The cumulative actual dose and actual dose intensity for each study drug (CC-122, ibrutinib, obinutuzumab) will be presented by dose cohort for each arm. The actual dose intensity is defined as the cumulative actual dose divided by the total length of treatment for the IP.

CC-122:

The cumulative actual dose of CC-122 is defined as the sum of all doses of CC-122 taken across the treatment period.

The cumulative expected dose of CC-122 is calculated as below:

- For the cycles on daily schedule of CC-122 (only applicable to Arm A subjects):

Expected dose = (stop date - start date of CC-122 administration +1) \times planned daily dose;

- For the cycles on 5/7 days schedule of CC-122:

$$\text{Expected dose} = \text{Planned daily dose} \times \left[\left\lfloor \frac{\text{Dur}}{7} \right\rfloor \times 5 + \min \left(5, \text{Dur} - \left\lfloor \frac{\text{Dur}}{7} \right\rfloor \times 7 \right) \right], \text{ where}$$

Dur is the treatment duration for CC-122.

Repeat this derivation for each planned dose (i.e. take into account the dose escalation but not the decrease due to AE) and sum up.

The Expected dose intensity for CC-122 is the cumulative expected dose divided by the total length of treatment duration for CC-122.

Ibrutinib (Arm B)

The cumulative actual dose of ibrutinib is the sum of all doses of Ibrutinib taken across the treatment period. The cumulative expected dose of ibrutinib is the (planned daily dose \times Ibrutinib treatment duration in days). The expected dose intensity for Ibrutinib is the planned daily dose – 420 mg/day.

Obinutuzumab (Arm C):

The cumulative actual dose of obinutuzumab is the sum of all doses of obinutuzumab taken across the treatment period. The cumulative expected dose of obinutuzumab is the sum of the planned dose per Table 10 in the protocol Section 8.2.2.3 based on the last visit which has been completed:

Last visit completed	Cycle 1 Day 1	Cycle 1 Day 2	Cycle 1 Day 8	Cycle 1 Day 15	Cycle 2 Day 1	Cycle 3 Day 1	Cycle 4 Day 1	Cycle 5 Day 1	Cycle 6 Day 1
Cumulative expected dose (mg)	100	1000	2000	3000	4000	5000	6000	7000	8000

The Expected dose intensity for obinutuzumab is the cumulative expected dose divided by the total length of treatment duration for obinutuzumab.

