12.1. PK and Exposure Response Analyses

During the Dose Escalation phase, intensive PK sampling will be performed in a minimum of 3 subjects in the first cycle in Arm A (Cycle 1, Days 1 and 15). PK parameters will be estimated based on the intensive PK population. Actual sampling times will be used in the calculations of PK parameters by using the non-compartmental analysis (NCA) method. Drug concentrations reported by the bioanalytical laboratory as Below the Quantification Limit (BQL) will be shown as BQL in the data listings. If >50% of results for a given timepoint and dose level, are reported as below the Low Limit of Quantification (LLOQ: 1.0 ng/mL), the mean, median and geometric mean are reported as LLOQ. In these scenarios, the other descriptive statistics are not calculated. Missing concentrations will be treated in PK calculations as if they were never drawn. If a concentration is missing (e.g., because no sample was taken, there was no valid result [including concentrations after dosing which are BQL], there was no detectable peak or the sample was lost), the concentration will not be imputed (i.e., it will remain missing). Every effort will be made to include all concentration data in the analysis. In the event that an actual sample collection time is missing for a certain time point, the planned time may be used for this time point instead.

Pharmacokinetic Plasma Concentrations:

CC-122 plasma concentrations from intensive sampling will be summarized by actual dose level, visit, and nominal time points. In general, geometric mean and the geometric CV (%) will be derived from non-zero concentration values. These results will be tabulated by dose cohort and treatment arms.

CV (%) is calculated as follows: $CV\% = \frac{StdDev}{mean} \times 100\ldots$

Geometric CV (%) is calculated as follows: $CV(\%) = 100 \times \sqrt{(\exp(\sigma^2) - 1)}$, where σ^2 denotes the variance of the log-transformed values.

The following figures will be provided by dose cohort using intensive PK population:

- Individual subject's concentration (linear scale and semi-logarithmic scale) over time spaghetti plot;
- Mean and \pm Std Dev of concentration (linear scale and semi-logarithmic scale) over time plot;

Note: Mean of 1 ng/mL at timepoint 0 will be imputed when more than 50% of values are below LLOQ.

Summary for Ibrutinib plasma concentration will not be performed due to limit data collected.

Pharmacokinetic Parameters:

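### CC-122 dose totals add mg of salt and mg of free base, and Arm A concentrations may pool two formulations, because the SAP never separates AIC from F6

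*Protocol*

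**What the plan says.** **Label basis (Protocol 8.1.1).** The 0.5, 1 and 3 mg AIC capsules are labelled as HCl salt and are "equivalent to 0.44, 0.88, and 2.64 mg CC-122 base free, respectively". F6 "strengths are based on CC-122 base free and are equivalent to 0.56, 1.13, 1.69, 2.25, 2.81, 3.38, 3.95 and 4.51 mg CC-122 HCl".

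**Exposure (Protocol 8.1.1).** In a separate crossover study, 18 healthy adults took a single 3 mg label dose. AUCinf was 16.29% higher on F6, and Cmax was "35.58% higher from the F-6 formulation as compared to that from the reference AIC formulation".

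**Who receives which (Protocol 8.1.1).** In Arm A, "subjects who start with AIC will continue to receive AIC", and F6 starters likewise stay on F6. In Arms B and C the 0.5 mg cohort uses AIC and F6 comes in at the 1.0 mg cohort. Reductions to 0.25 mg or below use AIC. Protocol 4.1 lets subjects in lower fixed-dose cohorts move up once the SRC approves.

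**Dose summaries (SAP 8.2).** "The cumulative actual dose of CC-122 is defined as the sum of all doses of CC-122 taken across the treatment period". No mg basis is stated.

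**Concentrations (SAP 12.1).** "CC-122 plasma concentrations from intensive sampling will be summarized by actual dose level, visit, and nominal time points". SAP 5.2.4 also groups the PK population by actual dose level. Intensive sampling is described for Arm A only, on Cycle 1 Days 1 and 15.

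The SAP text provided does not mention AIC, F6, salt, base or formulation. The list of changes in SAP 15 does not cover it either.

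**The concern.** A sum of mg means something only if every mg is the same quantity. Here 1 mg on an AIC label and 1 mg on an F6 label are different amounts of drug, and the protocol says so. A SAP written for the same amendment adds them without comment.

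Two outputs are exposed:

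- **Cumulative dose and absolute dose intensity.** A reader comparing columns, or reading an overall column, would take them as one scale.
- **Arm A concentrations.** CC-122 plasma concentration is a secondary endpoint (Protocol 3.2). SAP 15 drops the PK parameter analyses, so the concentration summaries, plots and listings are the CC-122 PK results that remain. They come from the one arm in which the protocol provides for both formulations at the same label doses.

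**Working it through.** **1. Reproduce the stated AIC contents.** Factor 0.88: 0.5 x 0.88 = 0.44; 1 x 0.88 = 0.88; 3 x 0.88 = 2.64. All three match.

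**2. Check the F6 pairs against that factor.** HCl per mg base runs from 0.56/0.5 = 1.12 to 1.13/1 = 1.13, and AIC gives 1/0.88 = 1.136. The pairs agree to within about 1.5%. At equal label, F6 therefore holds 12% to 13.6% more base.

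**3. Effect on a dose total.** The 5/7-day schedule gives 20 doses per 28 days. At 1.0 mg:
- AIC: 20 x 0.88 = 17.6 mg base
- F6: 20 x 1.00 = 20.0 mg base
- SAP 8.2: 20 mg for both

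Absolute dose intensity divides by treatment length, so it carries the same factor.

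**4. A subject who changes formulation.** Take one cycle at 0.5 mg AIC, then one at 1.0 mg F6.
- Label: 20 x 0.5 + 20 x 1.0 = 30 mg
- Base: 20 x 0.44 + 20 x 1.0 = 28.8 mg
- Ratio: 30/28.8 = 1.042

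**5. Relative dose intensity.** On one formulation the factor cancels: 16 of 20 doses is 0.80 on either scale. For the subject in step 4 with half the second cycle missed, it is (10 + 10)/30 = 0.667 in label mg and (8.8 + 10)/28.8 = 0.653 in base mg.

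**6. First step in Arms B and C.** From 0.5 mg AIC to 1.0 mg F6 is 2-fold on the label and 1.0/0.44 = 2.27-fold in base.

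**7. Arm A concentrations.** The documents do not give the share of F6 subjects, f, at a dose level. I assume f = 0.5, with a range of 0.25 to 0.75, and assume that the 3 mg healthy-adult ratios r carry over. Pooled mean relative to the AIC mean = 1 + f(r - 1); relative to the F6 mean, divide by r.
- r = 1.1629 (AUC): +8.1% (+4.1% to +12.2%) against AIC; -7.0% (-10.5% to -3.5%) against F6
- r = 1.3558 (Cmax): +17.8% (+8.9% to +26.7%) against AIC; -13.1% (-19.7% to -6.6%) against F6

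**8. Would conversion alone be enough for PK?** Normalising for base gives 1.1629 x 0.88 = 1.023 for AUC and 1.3558 x 0.88 = 1.193 for Cmax. Conversion removes most of the AUC gap and leaves about 19% in Cmax, so peak concentrations also need formulation identified.

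**The case against.** The strongest reply is that little turns on this, and much of it stands.

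- **The exposure figures do not belong to the dose tables.** A reader might infer that the SAP mixes groups differing by 16% to 36% throughout. The documents do not support that. Those figures are AUCinf and Cmax ratios from one 3 mg dose in healthy adults, and the SAP will analyse neither parameter. For summed mg the discrepancy is the salt/base factor, 12% to 13.6%.
- **Mixing in Arm A is permitted, not shown.** Protocol 8.1.1 says what happens to a subject who starts on each formulation. It does not say that both were used, or that both were sampled at one dose level in Cycle 1.
- **Starting-dose columns in Arms B and C begin on one formulation by design.** The NTD and MTD rest on DLT counts per cohort, which no unit conversion changes. A reader might take the 2.27-fold step as a dose-finding error. It is a feature of the design that follows from the contents given in Protocol 8.1.1.
- **Relative dose intensity, which SAP 8.3 uses in place of compliance, barely moves.**
- **Intra-subject escalation from 1.0 to 4.0 mg spreads the Arm A columns far more than 14%.** This is true, but it is visible variation on a stated scale. The unit mismatch is systematic and hidden.
- **A PK split may leave very small cells.** Sampling is planned in a minimum of 3 subjects, and SAP 12.1 calls the data limited. That argues for flagging formulation where cells are too small, not for leaving it out.

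Redacted SAP text and the table shells, which were not provided, could contain a split. The absence claimed here is for the text provided.

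**Conclusion.** The point holds at a limited size. As written, SAP 8.2 adds unlike units. Cumulative dose and absolute dose intensity combine two scales that differ by about 12% to 14% in three places:

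- Arm A columns, if both formulations were used;
- Arm B and C overall columns, which join the 0.5 mg AIC cohort to the F6 cohorts;
- totals for subjects who go from 0.5 mg AIC to a higher F6 dose, or from F6 to 0.25 mg or lower on AIC.

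The Arm A concentration summaries may pool AIC and F6 subjects. The size of that distortion is conditional on the assumed F6 share and on carrying single-dose healthy-adult ratios over to patients and other doses.

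Two further assumptions apply. The 0.88 factor is stated for the 0.5, 1 and 3 mg AIC strengths and is taken to hold at 0.25 mg and below. Subjects who escalate from the 0.5 mg cohort are taken to receive F6 at the higher dose; Protocol 8.1.1 implies this but does not spell it out for them.

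The material does not support a claim that dose-finding conclusions, DLT tables or relative dose intensity are materially wrong.

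**What to change.** - **SAP 8.2:** state the mg basis, and derive CC-122 cumulative dose and absolute dose intensity in free-base mg (AIC label x 0.88, F6 label unchanged).
- **SAP 12.1:** within each Arm A dose level, summarise concentrations by formulation, or at least flag formulation in tables, plots and listings where cells are too small to split.
- **Dose-level tables:** footnote the 0.5 mg cohorts in Arms B and C as AIC, and note that the step to 1.0 mg F6 is 2.27-fold in base.

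The cost is one derived variable, a formulation identifier in the PK outputs, and smaller cells in descriptive tables that are already sparse. This concerns reporting only; no change to dosing is proposed.
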